3.3.2. Benefit Assessment

Systemic sclerosis is an autoimmune disease with substantial excess morbidity and mortality, and for which no licensed disease modifying treatments are available. There is pre-clinical evidence to suggest that GSK2330811 may be effective in treating the underlying disease process and therefore in ameliorating the signs and symptoms of SSc in an individual participant receiving GSK2330811. However, should there be any direct benefit to a participant in the study, this may be limited by the short duration of treatment in an otherwise chronic disease.

3.3.3. Overall Benefit:Risk Conclusion

Balanced against the measures taken to minimise them, the potential haematologic and other risks to participants in this POM study of GSK2330811 are justified by need to develop more effective treatments for SSc.

4. OBJECTIVES AND ENDPOINTS

Objectives	Endpoints

Primary
 
 To evaluate the safety and tolerability of repeat subcutaneous doses of GSK2330811 in participants with dcSSc 	
 Adverse event reporting Laboratory safety data (clinical chemistry, haematology, urinalysis) Vital signs (blood pressure, heart rate, body temperature) 12 lead ECGs

Secondary
 
 To evaluate the pharmacokinetic profile of repeat subcutaneous doses of GSK2330811 in participants with dcSSc 	
 Plasma concentrations of GSK2330811 and derived pharmacokinetic parameters (e.g C_{trough}, apparent clearance (CL/F) and apparent volume of distribution (V_{ss}/F))

 To assess the target engagement of repeat subcutaneous doses of GSK2330811 in the blood of participants with dcSSc 	
 Serum levels of total OSM Serum levels of free OSM

 To assess the potential for anti-drug antibody formation following repeat subcutaneous doses of GSK2330811 in participants with dcSSc 	
 Incidence and titres of anti-GSK2330811 antibodies

Objectives	Endpoints

Exploratory
 
 To explore the pharmacology of repeat subcutaneous doses of GSK2330811 and its effects on biomarkers of fibrosis, inflammation and vasculopathy in the blood and skin of participants with dcSSc 	
 Endpoints may include (but are not limited to): 
 Skin Biopsies: Change from baseline in mRNA expression and protein levels of selected markers chosen to reflect fibrosis, vasculopathy and tissue inflammation (e.g. αSMA, CD31 and CD3 respectively) at Day 85 (Week 12) Blood: Change from baseline over time in CRP, other soluble protein markers (e.g. collagen turnover, VEGF and IL-6) and mRNA expression

 To explore the PK and target engagement of repeat subcutaneous doses of GSK2330811 in the skin of participants with dcSSc using suction induced blisters 	
 Endpoints may include (but are not limited to): 
 Levels of GSK2330811 in blister fluid measured anytime between Day 57 and Day 85 (Week 8 and Week 12) Levels of OSM in blister fluid measured anytime between Day 57 and Day 85 (Week 8 and Week 12)

 To explore the effect of repeat subcutaneous doses of GSK2330811 on the extent of skin involvement in participants with dcSSc 	
 Change from baseline in modified Rodnan skin score (mRSS) over time

 To explore the effect of repeat subcutaneous doses of GSK2330811 on lung function in participants with dcSSc 	
 Rate of change in forced vital capacity (FVC) Change from baseline in FVC

 To explore the effect of repeat subcutaneous doses of GSK2330811 on SSc related symptoms, physical function and disease activity in participants with dcSSc 	
 Change from baseline in Scleroderma Health Assessment Questionnaire (SHAQ) Change from baseline in Physician Global Assessment of Disease Activity (PhGA) Change from baseline in Patient Global Assessment of Disease Activity (PtGA) Composite Response Index for Systemic Sclerosis (CRISS)

Objectives	Endpoints

 To characterise the mechanisms of any observed haematological effects of GSK2330811. 	
 Change from baseline in selected blood markers related to mechanisms of anaemia and thrombocytopenia.

[figure not shown]
5. STUDY DESIGN

5.1. Overall Design

This is a multi-centre, randomised, double blind (sponsor open), placebo-controlled, repeat-dose, proof of mechanism study of subcutaneous administrations of GSK2330811 in males and females with dcSSc.

The study includes two sequential cohorts. Cohort 1 is planned to consist of at least 4 participants and will evaluate a repeat-dose predicted to provide sub-maximal inhibition of OSM, leading to a dose escalation decision once at least 4 participants have reached the end of the treatment period (see Section 7.2). Cohort 2 will then evaluate a repeat-dose, predicted to provide maximal inhibition of OSM, to test POM. The study design, for both cohorts, is depicted in Figure 1.

Figure 1 Study Schematic

- Participants who consent will attend the clinical facility for screening and if eligible will enter the treatment period of the study within 42 days.
- The screening period will be at least 28 days for WOCBP to allow for a minimum 28 day interval between the screening and Day 1 pregnancy tests.
- Participants will be randomised in a 3:1 ratio within each cohort to GSK2330811 and placebo respectively. In cohort 2 treatment allocation will be stratified according to mycophenolate concomitant medication status (treated or non-treated).
- Participants will attend the clinical facility to receive a subcutaneous dose of GSK2330811 or placebo on Day 1 and then every other week until the sixth and final dose at the Day 71 (Week 10) visit.
- A Data Review Committee (DRC) will be responsible for determining progression from cohort 1 to cohort 2 as described in Section 7.2.
- Interim analyses will be conducted during cohort 2. The rationale, conduct and potential outcomes of these are described in Section 10.3.3.
- Study safety monitoring will be undertaken in a blinded manner by the Sponsor Safety Review Team (SRT) as described in Appendix 3. The Study Medical Monitor will also continuously review adverse events and laboratory tests for individual participants during the conduct of the study to ensure individual participant monitoring.
- Skin biopsies will be collected to assess GSK2330811 pharmacology and biomarkers at the site of action. Two punch biopsies will be collected from involved skin, on the forearm of participants, on both Day 1 and during the Day 85 (Week 12) visit window.
- A skin suction blister procedure will be performed on involved skin on the forearm of participants at selected sites at anytime between the Day 57 (Week 8) visit and the Day 85 (Week 12) visit inclusive. This will be optional for participants and only performed in participants enrolled in cohort 2.
- After the treatment period, participants will enter a follow-up period of approximately 16 weeks.
- In addition to study visits, weekly home FVC monitoring will be undertaken during the study (from screening until Day 197 (Week 28)).

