5.2. Number of Participants, Treatment Arms and Duration

Participants with dcSSc, with active disease and a disease duration of ≤ 60 months, will be enrolled. A minimum of approximately 24 participants and a maximum of 40 participants will be randomised across two cohorts. The duration of the study, including screening, will be up to 34 weeks for participants.

Participants will be dosed subcutaneously at one of two dose levels every other week for 10 weeks with either GSK2330811 or placebo.

For cohort 1, an initial 4 participants will be randomised to either GSK2330811 or placebo. If a decision is made to expand cohort 1 a further 4 participants will be entered into cohort 1. For cohort 2, a minimum of approximately 20 participants will be randomised. Participants from Cohort 1 will not be eligible to participate in Cohort 2.

A participant in cohort 1 is evaluable for dose escalation if they have received at least 4 doses of GSK2330811 or placebo, have reached the end of the treatment period and there is a standard haematology result from at least one of the Day 71 (Week 10), Day 85 (Week 12) or Day 113 (Week 16) visits. If any participant in cohort 1 cannot be evaluated for dose escalation, additional participants may be recruited and assigned to the same treatment sequence at the discretion of the sponsor up to a maximum of 8 evaluable participants.

A participant in cohort 1 or cohort 2 is considered evaluable for study endpoints if they have received at least 4 doses of GSK2330811 or placebo and have biopsies at both the Day 1 and the Day 85 (Week 12) assessment. Additional participants may be entered into the study at the discretion of the sponsor up to a maximum of 40 randomised participants in the study overall.

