7.1. Treatments Administered

Syringes containing GSK2330811 or placebo will be prepared at the study site by an unblinded pharmacist or designee. Placebo will be sourced locally by the site while GSK2330811 will be provided by GSK. GSK2330811 or placebo will be administered by subcutaneous injection in to the abdomen, thigh or upper arm by the investigator or designee. Participants will remain at the clinic for observation for at least 30 minutes after each dose has been administered. See the Study Reference Manual (SRM) for further details.

Study Treatment Name:	GSK2330811	Placebo
Dosage formulation:	Solution for injection; 50 mM Sodium Acetate, 0.05 mM EDTA, 1.0% Arginine, 51 mM Sodium Chloride, pH 5.5 with 0.02% polysorbate 80	Normal Saline (0.9% w/v Sodium Chloride)
Unit dose strength(s)/Dosage level(s):	1.2mL fill with 1mL extractable volume at 100 mg/mL	Not applicable
Storage:	Store between 2-8°C, protect from light	As recommended by supplier

Study Treatment Name:	GSK2330811	Placebo
Route of Administration:	SC injection only	SC injection only
Dosing instructions:	Administered by investigator or designee. Cohort 1 100 mg dose 1 x 1ml injected via needle and syringe Cohort 2 300 mg dose 3 x 1ml injected via needle and syringe If a dose lower than 300 mg is required then the volume injected will be reduced accordingly.	Administered by investigator or designee. Injection volume and number of injections will match active doses administered.
Packaging and Labeling:	Study Treatment will be provided in vials and packed in 1 vial per carton. Each vial and carton will be labelled as required per country requirement.	
Manufacturer:	GSK	To be sourced locally

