5. CONSIDERATIONS FOR DATA ANALYSES AND DATA HANDLING CONVENTIONS

5.1. Study Treatment Display Descriptors

Treatment Group Descriptions			
RandAll NG Data Displays for Reporting			
Code	Description ^[3]	Description ^[2] Order ^[1]	
А	GSK2230811 100 mg SC - PARALLEL	GSK2330811 100 mg	2
В	GSK2230811 300 mg SC - PARALLEL	GSK2330811 300 mg	3
Р	Placebo - PARALLEL	Placebo	1

NOTES:

1. Order represents treatments being presented in TFL, as appropriate.

2. If there is no space for the full drug name, and the full drug name is in the title or elsewhere on the output then the dose amount (i.e. 100mg or 300mg) may be used with consultation with statistician

3. This RAP instruction corrects a mistake in the Treatment Description field in the RANDALL NG.

Treatment comparisons will be displayed as follows using the descriptors as specified:

- 1. GSK2330811 100 mg vs Placebo
- 2. GSK2330811 300 mg vs Placebo

Or, in short form when full drug name is shown in title or elsewhere on table, listing or Figure and after consultation with statistician:

- 1. 100 mg vs Placebo
- 2. 300 mg vs Placebo

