13.1.5. Statistical Analyses / Methods

Details of the planned displays are provided in Appendix 12 and will be based on GSK Data Standards and statistical principles.

The endpoints / variables defined in Section 13.1.1 will be summarised using descriptive statistics, graphically presented (where appropriate) and listed.

Longitudinal model

The ratio to baseline for the following systemic biomarkers will be analysed using a Bayesian MMRM analysis using the log transformed data including only the placebo and GSK2330811 300mg arms:

- Pro-C3
- Pro-C6
- PINP
- ELF
- COMP
- PIIINP
- IL-6
- MCP-1 (Rename MCP-1 as CCL2 for displays)
- CCL-18

Non-informative priors will be used in these analyses, specifically the prior for the regression coefficient will be normally distributed with mean 0 and a variance of 10^6 . The variance-covariance matrix for the within subject error across the visits will use an inverse-Wishart prior distribution, consisting of the identity matrix and the degrees of freedom will be the number of visits included in the model.

The models will be adjusted for the following covariates: MMF use at day 1, baseline value, treatment, visit, treatment by visit and baseline by visit interactions.

201247

The change from baseline within each treatment group and the difference in the change from baseline across the treatment groups (GSK2330811 300mg – placebo) will be calculated and are back transformed to give the ratio to baseline and the ratio of the change relative to placebo respectively.

Posterior medians and equal tailed 95% credible intervals will be presented. In addition, the probability the ratios are <1 and fold changes (Posterior Medians, as ratio < 1 then fold change is -1/ratio otherwise fold change is ratio) will also be calculated. The line plot of the adjusted posterior medians \pm credible intervals at each visit will be presented.

ANCOVA

The ratio to baseline of log transformed and change from baseline of linear data for the following skin histology and gene expression mRNA sequencing endpoints will be analysed using a Bayesian ANCOVA analysis including only the placebo and GSK2330811 300mg arms:

- Alpha SMA (Excluding Insufficient samples)
- COMP
- CCL2
- 2GSSc
- Disease Signatures GSVA Scores (Upregulated and Downregulated)
- Lung Fibrosis Signature GSVA Score
- Cell Modular Signatures GSVA Scores (Fibrosis, M1-Macrophage and M2-Macrophage)

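### The exploratory 300 mg versus placebo models, as written, include cohort 1 placebo participants who were never randomised against 300 mg, and no model has a cohort term

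*Protocol*

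**What the plan says.** **Design.** Protocol 5.1: "The study includes two sequential cohorts", and "Participants will be randomised in a 3:1 ratio within each cohort to GSK2330811 and placebo respectively". It adds: "In cohort 2 treatment allocation will be stratified according to mycophenolate concomitant medication status". Under Protocol 7.2, the move to cohort 2 waits until four evaluable cohort 1 participants have reached Day 85 and the Data Review Committee has reviewed the data. Protocol 5.2 bars cohort 1 participants from cohort 2. It also allows cohort 1 to grow: "If a decision is made to expand cohort 1 a further 4 participants will be entered into cohort 1".

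**Analysis.** SAP 5.1 has one placebo code for the whole study and plans the comparison "GSK2330811 300 mg vs Placebo". In SAP 13.1.5 the Bayesian MMRM, ANCOVA and joint model are each fitted "including only the placebo and GSK2330811 300mg arms". The MMRM adjusts for Day 1 mycophenolate use, baseline, treatment, visit, and the treatment-by-visit and baseline-by-visit interactions. The ANCOVA adjusts for mycophenolate, baseline and treatment, and the joint model uses the corresponding by-endpoint terms. SAP 14.1.5 reuses the longitudinal model for mRSS, HAQ-DI and laboratory FVC. It analyses CRISS with a two-group rank model that lists no covariates.

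**Cohort.** SAP 5.2 derives a cohort variable for the blinded safety review outputs. It appears in no model, and nothing restricts placebo to cohort 2. The heat plots in SAP 13.1.5 have three columns, with placebo as one of them.

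**The concern.** The protection that randomisation gives to a 300 mg versus placebo contrast exists inside cohort 2 only. A cohort 1 placebo participant entered earlier, under a separate schedule without mycophenolate stratification, and could not have been assigned 300 mg. The SAP narrows the active side of the contrast to one cohort's dose but leaves the control side spanning both. Any difference between cohorts in how placebo participants change from baseline is then counted as treatment effect.

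Protocol 5.1 says cohort 2 exists to test proof of mechanism, and these models supply its between-group estimates and posterior probabilities. A reader given one pooled figure cannot tell how much of it rests on the randomised comparison. The protocol's own precision statement (10.1) counts 15 versus 5, which are the cohort 2 numbers alone.

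**Working it through.** **Inputs.** Allocation 3:1 in each cohort (Protocol 5.1). Cohort 1 of 4, expandable to 8 (5.2, 7.2). Cohort 2 of about 20 up to 36, with at most 40 randomised overall (5.2, 10.1). SD of log(PIIINP) 0.521, two-sided 5%, and a stated 95% half-width of 0.565 (10.1). Exact 3:1 splits are assumed.

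**Step 1: reproduce the protocol's figure.** Half-width = t(0.975, n1+n0−2) × SD × √(1/n1 + 1/n0). For 15 versus 5: 2.101 × 0.521 × 0.5164 = 0.565, which matches.

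**Step 2: share of controls outside the randomised comparison, and the precision gained by pooling.** The share is s = cohort 1 placebo ÷ all placebo. Half-widths use the Step 1 formula.

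| Cohorts 1 + 2 | 300 mg | Placebo, cohort 2 + cohort 1 | s | Half-width, pooled | Half-width, cohort 2 only | Ratio |
|---|---|---|---|---|---|---|
| 4 + 20 | 15 | 5 + 1 | 1/6 = 17% | 0.527 | 0.565 | 1.07 |
| 8 + 20 | 15 | 5 + 2 | 2/7 = 29% | 0.497 | 0.565 | 1.14 |
| 4 + 36 | 27 | 9 + 1 | 1/10 = 10% | 0.392 | 0.408 | 1.04 |
| 8 + 32 | 24 | 8 + 2 | 2/10 = 20% | 0.399 | 0.434 | 1.09 |

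The narrower pooled interval comes wholly from the non-concurrent participants.

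**Step 3: bias.** Let D be the cohort 1 minus cohort 2 difference in adjusted placebo change. The pooled placebo mean equals the cohort 2 placebo mean + s × D, so the contrast is shifted by −s × D. D is not in the documents, so assumed values are used:

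| Cohorts | Shift if D = 0.5 SD | Shift if D = 1 SD |
|---|---|---|
| 4 + 20 | 0.08 SD | 0.17 SD |
| 8 + 20 | 0.14 SD | 0.29 SD |
| 4 + 36 | 0.05 SD | 0.10 SD |
| 8 + 32 | 0.10 SD | 0.20 SD |

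Relative to sampling error, with D = 1 SD: for 4 + 20 the shift is 0.521/6 = 0.087 against an SE of 0.521 × √(1/15 + 1/6) = 0.252, or 0.35 SE. For 8 + 20 it is 0.521 × 2/7 = 0.149 against 0.238, or 0.62 SE.

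**Step 4: would a cohort term do the same job?** In a single-visit linear model, yes. With 15, 5 and 1 or 2 participants, a fixed cohort effect takes the weight of each cohort 1 placebo participant to zero and the SE returns to 0.269, as in the cohort 2-only fit.

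In the MMRM a cohort main effect is not enough. Take four post-baseline visits (the blood biomarker schedule), cohort 1 with 1 placebo and 3 active, cohort 2 with 5 and 15, and compound symmetry. The main effect removes only the average over visits. The cohort 1 placebo participant therefore keeps 1/6 × 3/4 = 12.5% of the placebo weight at the target visit, against 16.7% with no cohort term. A constant shift cancels, because the other three visits each carry 1/6 × 1/4 = 4.2% with the opposite sign. A shift that varies by visit does not cancel. With a cohort-by-visit term the weight is zero.

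**The case against.** **Scope.** Primary and secondary endpoints have no planned statistical analysis (SAP 2.4.1, 2.4.2), and Protocol 3.1 disclaims formal hypothesis testing. Every affected model is exploratory estimation, and one or two placebo participants are planned in cohort 1. This stands and limits the weight of the point.

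**Inference.** The SAP never says that placebo is pooled across cohorts. That follows from the single code, the model wording and the absence of any restriction. If cohort 2 placebo alone was intended, the SAP needs to say so. SAP 5.5.1 allows further covariates but does not name cohort.

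**Size of D.** The models, apart from CRISS, analyse change or ratio to baseline with baseline and mycophenolate as covariates, so a constant level shift largely cancels. Protocol 9.1.5 asks for the same mRSS assessor throughout for each participant. D may therefore be small, and 0.5 to 1 SD is illustrative. The covariates do not, however, adjust for calendar time, and SAP 13.1.5.1 makes mycophenolate the first covariate considered for removal if a model fails to converge.

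**Stronger readings the documents do not support.**
- A reader might take the C1M assay change between cohorts (SAP 13.1.1.1) as proof that drift enters the treatment effect. C1M is not a modelled endpoint, and the two assays are summarised and plotted separately.
- A reader might conclude from Protocol 5.2 that cohort 1 replacements escape randomisation, since "additional participants may be recruited and assigned to the same treatment sequence at the discretion of the sponsor". That provision is conditional, and Protocol 7.3 says all participants are centrally randomised on Day 1. The point does not need it.
- Placebo is one injection in cohort 1 and three in cohort 2 ("Injection volume and number of injections will match active doses administered", Protocol 7.1). The documents give no route by which this would alter serum or skin biomarkers.

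**Conclusion.** The point holds for the exploratory biomarker and efficacy estimates and goes no further. As written, 10 to 29% of the planned control group was never randomised against 300 mg, and no model accounts for cohort. The resulting bias is that share times an unknown between-cohort difference in adjusted placebo change: 0.05 to 0.29 SD if the difference is 0.5 to 1 SD, and nil if there is none.

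It would be wrong to infer that the treatment comparison is shown to be biased, or that the safety objective is undermined. The documents record no between-cohort difference in any modelled endpoint.

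The result rests on reading the single placebo code as covering both cohorts and on exact 3:1 splits at the planned sizes. Per-protocol exclusions would change the counts. The half-widths are unadjusted t-interval approximations to the planned credible intervals. The change is worth making because it is cheap and analyses the data within the unit by which the trial randomises.

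**What to change.** In SAP 13.1.5 and 14.1.5, for every 300 mg versus placebo model (MMRM, ANCOVA, joint model, CRISS), add a fit restricted to cohort 2. Report its estimate and interval, or for CRISS its posterior probability, beside the pooled-placebo result. State in advance that the cohort 2 fit is the randomised comparison and governs interpretation if the two differ. State also which cohorts the pooled placebo group contains.

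If a cohort term is preferred, keep all three arms and include cohort-by-visit in the MMRM; a cohort main effect alone does not isolate cohort 2. By the same reasoning the joint model would need cohort-by-endpoint. The CRISS rank model lists no covariates, so it needs the restricted fit.

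**Cost.** A few sentences in the SAP and a second run of existing programs, since cohort can already be derived under SAP 5.2. Intervals are about 4 to 14% wider; at 15 versus 5 the half-width is the 0.565 that the protocol itself quotes. Models with about five placebo participants, or fewer after per-protocol exclusions, are more likely to meet the non-convergence steps in SAP 13.1.5.1. Keeping the pooled fit as a companion leaves a result to report in that case, with its limitation stated.

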5.2. Number of Participants, Treatment Arms and Duration

Participants with dcSSc, with active disease and a disease duration of ≤ 60 months, will be enrolled. A minimum of approximately 24 participants and a maximum of 40 participants will be randomised across two cohorts. The duration of the study, including screening, will be up to 34 weeks for participants.

Participants will be dosed subcutaneously at one of two dose levels every other week for 10 weeks with either GSK2330811 or placebo.

For cohort 1, an initial 4 participants will be randomised to either GSK2330811 or placebo. If a decision is made to expand cohort 1 a further 4 participants will be entered into cohort 1. For cohort 2, a minimum of approximately 20 participants will be randomised. Participants from Cohort 1 will not be eligible to participate in Cohort 2.

A participant in cohort 1 is evaluable for dose escalation if they have received at least 4 doses of GSK2330811 or placebo, have reached the end of the treatment period and there is a standard haematology result from at least one of the Day 71 (Week 10), Day 85 (Week 12) or Day 113 (Week 16) visits. If any participant in cohort 1 cannot be evaluated for dose escalation, additional participants may be recruited and assigned to the same treatment sequence at the discretion of the sponsor up to a maximum of 8 evaluable participants.

A participant in cohort 1 or cohort 2 is considered evaluable for study endpoints if they have received at least 4 doses of GSK2330811 or placebo and have biopsies at both the Day 1 and the Day 85 (Week 12) assessment. Additional participants may be entered into the study at the discretion of the sponsor up to a maximum of 40 randomised participants in the study overall.

